#### 3.4.2.2 IR Leading to Discontinuation of Treatment, Anaphylaxis, or Meeting Individual Subject sUA Discontinuation Criteria

The estimand for the secondary endpoints related to IRs leading to discontinuation and meeting sUA discontinuation criteria is defined by the following:

Population	Safety Analysis Set for the cohort chosen to be most desirable for infusion
Endpoint	Incidence of subjects experiencing IR leading to discontinuation of treatment, anaphylaxis, or meeting Individual Subject sUA Discontinuation Criteria (two consecutive pre-infusion sUAs $> 6$ mg/dL  Time to any of the following events: IR leading to discontinuation of treatment, anaphylaxis, or meeting Individual Subject sUA

	Discontinuation Criteria (two consecutive pre-infusion sUAs $> 6$ mg/dL)
ICE	Early discontinuation of pegloticase
ICE Strategy	Only events that occur while the subject is receiving study pegloticase will be counted
Population-level Summary	Proportion of subjects who experience an IR (including anaphylaxis) related to pegloticase between Day 1 and Week 24 Median time to the first event

The proportion of subjects experiencing any of the following events (composite endpoint and for each individual component) will be summarized descriptively along with a two-sided 95% exact (Clopper-Pearson) confidence interval:

The time to subjects experiencing any of the following events:

- IR leading to discontinuation of treatment
- Anaphylaxis or
- Meeting Individual Subject sUA Discontinuation Criteria

will be summarized descriptively for the safety analysis set as a composite endpoint by assigned infusion duration group. Kaplan Meier (KM) estimates of the time to event from Day 1 will be reported along with the corresponding quartiles and a 95% CI for the median time if there are sufficient number of events to perform the analysis. An estimate of the cumulative incidence rate by Week 24 will also be calculated. For the analysis of the composite endpoint, subjects who do not experience any of the aforementioned events will be censored at the time of last infusion.

[figure not shown]
Time to event to each individual component of the composite endpoint will also be summarized descriptively. To account for the competing events nature of these events, the cumulative incidence function will be determined and estimates of the cumulative incidence by Week 24 and median time to event for each event will be summarized with a 95% CI for the median time (if available). Subjects who do not experience any of the competing events or the event of interest will be censored at the date of their last infusion.

A competing event is defined as any of the components of the composite endpoint or discontinuation from treatment for any reason. Other competing events may be included in the analysis, as needed.

The time to an event will be calculated by date of event – date of first dose of treatment + 1. Patients who do not experience an event will be censored at time given by date of last dose of treatment - date of the first dose of the treatment + 1.

Events of anaphylaxis and IRs are collected as “reported events” and “adjudicated events”. For all relevant endpoints, separate analyses will be created for reported events and adjudicated events.

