15. Subjects will take folic acid 1 mg orally every day beginning at Week -4 (the start of MTX) until prior to the End of Pegloticase Infusions Visit (if applicable) or the Week 24/End of Study/Early Termination. Prescriptions are to be filled at a local pharmacy, as needed.
16. IR prophylaxis: fexofenadine (180 mg orally) administered the day before each infusion; fexofenadine (180 mg orally) and acetaminophen (1000 mg orally) administered on the morning of each infusion; and methylprednisolone (125 mg IV) will be administered over an infusion duration between 10 – 30 minutes, immediately prior to each pegloticase infusion.
17. For all subjects, serum samples for pegloticase PK analysis will be collected approximately 15 minutes to 2 hours after the end of infusion on Day 1; prior to infusion and approximately 15 minutes to 2 hours after the end of infusion at the Weeks 2, 6, 12, 20. An additional PK sample will be collected at Week 24 End of Study/Early Termination Visits.
18. Serum samples for measurement of sUA levels will be collected at the Screening Visit, the Week -4 Visit and the Week -2 Visit during the Run-in Period; within 48 hours prior to each pegloticase infusion and after the end of each pegloticase infusion prior to discharge from the site during the Pegloticase + MTX Period on Day 1, at the Weeks 2, 6, 10, 12, 14, 20 and 22; within 48 hours prior to each pegloticase infusion at Weeks 4, 8, 16, 18. Additional serum samples for sUA levels will be collected at non-infusion Visits at the End of Pegloticase Infusions Visit (if applicable) and the Week 24/End of study/Early Termination Visit and 3-

month Follow-up Visit. A subject with sUA level  $>6$  mg/dL (based on the local or central laboratory) at 2 consecutive study visits, beginning with the Week 2 Visit, will be discontinued from pegloticase treatment and remain on study. If a subject's previous visit pre-infusion sUA was  $<6$  mg/dL – sUA result is not required for the following infusion visit (local pre-infusion sUA may be drawn at the same time as central pre-infusion sample). If a subject's previous visit pre-infusion sUA was  $>6$  mg/dL – local sUA is required to be resulted (within 48 hours) to confirm stopping criteria was not met. See Section 9.6.2.1 and the Laboratory Manual for instructions for alternate scenarios. In the event of an AE suspected to be an IR, a serum sample will be collected at that time or at the subsequent visit for evaluation of pegloticase antibodies.

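### Censoring event-free completers on their own Week 22 infusion day can bias the Week 24 incidence of the composite secondary endpoint upward (minor)

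*SAP*

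**What the plan says.** SAP 3.4.2.2 plans a Kaplan-Meier analysis from Day 1 and adds: "An estimate of the cumulative incidence rate by Week 24 will also be calculated". Its censoring rule for the composite is that "subjects who do not experience any of the aforementioned events will be censored at the time of last infusion". For the component cumulative incidence functions: "Subjects who do not experience any of the competing events or the event of interest will be censored at the date of their last infusion". There, "A competing event is defined as any of the components of the composite endpoint or discontinuation from treatment for any reason".

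Times run on actual dates: "The time to an event will be calculated by date of event" minus the first dose date plus 1, and censoring times use the last dose date in the same way. SAP 3.1.1 sets weeks as the timescale but does not move times to nominal visits.

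The last of the 12 infusions is at Week 22 (SAP 1.1.2). Its target is Day 155, and Week 24 is Day 169 (SAP 3.1.5, Table 1). Visits may fall 3 days either side of target (note to Protocol Figure 9.1), so Week 22 infusions given in window span Days 152 to 158.

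The sUA component is worded in SAP 3.4.2.2 as "two consecutive pre-infusion sUAs" above 6 mg/dL. Protocol 9.6.2.1 requires a result before dosing when the previous pre-infusion value was above 6. A subject high at Weeks 20 and 22 is thus identified at Week 22 and not infused. Neither document says which date that event carries.

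**The concern.** A completer infused on Day 154 has already passed the last occasion on which the sUA criterion can be met. The planned rule removes that subject from the risk set on Day 154. If another subject then meets the criterion at a Day 157 visit, Kaplan-Meier divides that event by the few completers still awaiting infusion. In effect it applies their hazard to subjects who had already passed the same check. The censoring is tied to the visit process, so it is not independent of the event, and the error runs upward.

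The report would show, for the same events, a crude proportion and a higher Week 24 incidence. Part of the gap would reflect only the day of the window on which people attended.

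**Working it through.** **The plan's own figure.** The documents give none for this analysis. The only design figure is the sample-size statement in SAP 1.1.3, which fixes n = 110. It reproduces: the exact two-sided 95% upper limit is 12.67% for 7/110 and 13.83% for 8/110, so at most 7 events are needed, and P(X ≤ 7) at a 5% rate is 0.814.

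**Worked example (assumed counts).** Take 110 subjects with 15 earlier events, then 5 event-free discontinuations, leaving 90 at the Week 22 visit. One of these 90 meets the sUA criterion there, and the event is dated at the visit. The 90 visits fall on Days 152 to 158 as 4/8/18/30/16/9/5. Survival before Week 22 is 95/110 = 0.8636. Incidence at Week 24 is 1 − 0.8636 × (1 − 1/r), where r is the number still at risk on the event day.

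| Event day | r | Planned rule | Completers held to Day 169 |
|---|---|---|---|
| 152 | 90 | 14.6% | 14.6% |
| 155 | 60 | 15.1% | 14.6% |
| 156 | 30 | 16.5% | 14.6% |
| 157 | 14 | 19.8% | 14.6% |
| 158 | 5 | 30.9% | 14.6% |

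The crude proportion is 16/110 = 14.5% in every row. Days 152 to 155 hold 60 of the 90 visits and add at most about half a point of excess. The large figures come from the last two days. Averaged over visit days, the step for this event is 0.8636/90 × (4/90 + 8/86 + 18/78 + 30/60 + 16/30 + 9/14 + 5/5) = 0.8636/90 × 3.04 = 2.9 points, against 0.8636/90 = 0.96 with the full risk set. With evenly spread visit days the multiplier is 1/7 + 1/6 + 1/5 + 1/4 + 1/3 + 1/2 + 1 = 2.59. If the late event falls on the last subject at risk, the estimate goes to 100%.

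**Simulation by Week 22 hazard (assumed inputs).** n = 110, 1,500 trials per setting, sUA hazard 1.8% per visit at Weeks 4 to 20, other discontinuation 0.5% per visit, event dated at the visit. Excess is the planned rule minus completers held to Day 169, in points.

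| Visit days | Week 22 hazard | Mean excess | Median excess | Trials over 2 points |
|---|---|---|---|---|
| All on target | 0.5%, 1%, 2% | 0.0 | 0.0 | 0% |
| Peaked, ±3 | 0.5% | 0.9 | 0.0 | 10% |
| Peaked, ±3 | 1% | 1.7 | 0.1 | 22% |
| Peaked, ±3 | 2% | 3.4 | 0.9 | 39% |
| Uniform, ±3 | 0.5% | 0.7 | 0.0 | 11% |
| Uniform, ±3 | 1% | 1.3 | 0.2 | 21% |
| Uniform, ±3 | 2% | 2.6 | 1.3 | 42% |

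In the peaked 1% setting, dating the event 1 or 2 days before the visit cuts the mean excess to about 0.5 or 0.2 points.

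**Simulation by composite rate (assumed inputs).** n = 110, all events sUA events, other discontinuation 0.6% per visit, visit scatter from ±1 to ±3 days, flat or front-loaded hazard.

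| | 10% composite | 20% composite |
|---|---|---|
| Mean excess, dated at visit | about 0.3 to 2 | about 0.4 to 4 |
| Mean excess, dated 0 to 2 days earlier | about 0.1 to 1 | about 0.2 to 2 |
| Median excess, dated at visit | 0 to 0.5 | 0 to 1.5 |
| SD, planned rule | 3.0 to 5.8 | 4.1 to 8.4 |
| SD, completers held to Day 162 | about 2.9 | about 3.9 |
| Trials with a Week 22 sUA event | 27 to 67% | 45 to 87% |

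Monte Carlo error at the upper end is one or two tenths of a point, so second decimals carry no meaning.

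**Component functions.** Because discontinuation for any reason is a competing event, completers are the only subjects censored. If they stay at risk through the Week 22 visits, the sUA function equals the crude sUA proportion. Under the planned rule it can exceed it.

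**The case against.** The strongest objection concerns size. The mean is driven by uncommon events on Days 157 and 158, and the median excess is often near zero, especially with a front-loaded hazard. The deciding sample may be drawn up to 48 hours before the infusion, so dating by sample is at least as natural as dating by visit, and it roughly halves the average. All rates and visit scatter are assumed. All of this stands.

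The estimand's population-level summaries are a proportion and a median time, so the Week 24 incidence is an added descriptive figure. This also stands.

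The on-treatment rule ("Only events that occur while the subject is receiving study pegloticase will be counted") could be read as excluding an event found when the infusion is withheld. That reading would remove sUA events at every visit and empty the component, so it cannot be what is meant. Dating the event at the last infusion received would remove the upward bias, but the SAP does not say so. Rounding to the nearest week would not fully remove it: Day 158 is 158/7 = 22.57 weeks, which rounds to 23, while Day 157 is 22.43.

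A reader might also infer that every component function would match its crude proportion once completers stay at risk. That does not follow. Infusion reaction and anaphylaxis overlap, and a subject can count in two crude proportions but only once as a first event.

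**Conclusion.** The point holds as a minor flaw in the analysis text. The censoring rule does not fit a Week 24 landmark, and it can bias the composite incidence and the sUA component function upward and make them more variable. Under the stated assumptions the average excess is roughly 0.3 to 2 points at a 10% composite rate and 0.4 to 4 points at 20% with visit dating, and about half that with sample dating. In these calculations it is exactly zero when no sUA event occurs at Week 22 or when all visits are on schedule.

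Two stronger readings are not supported. First, a reader might infer that the endpoint's main results are compromised. The crude proportion and its exact interval are unaffected, the median time is ordinarily not reached at these rates, and no decision rests on the Week 24 figure. Second, a reader might infer that a high pair at Weeks 22 and 24 would create events after everyone has been censored. SAP 3.4.2.2 words the criterion as pre-infusion, and Protocol 2.1, footnote 18, places Week 24 among the samples of which it says "Additional serum samples for sUA levels will be collected at non-infusion Visits". The documents therefore point against counting Week 24.

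**What to change.** Change the wording of SAP 3.4.2.2 in two places.

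1. For the composite and the component functions, keep subjects who received the Week 22 infusion event-free at risk until every Week 22 visit is past, by censoring them on a common administrative day. Day 162 lies beyond the 3-day window. It is borrowed from the upper limit for Week 22 in SAP Table 1, which is a visit-reassignment limit and not an infusion window. Day 169 (Week 24) would also serve. Leave all other censoring and all actual dates unchanged.
2. Date the sUA event at the second consecutive pre-infusion value above 6 mg/dL, and state that it counts as on-treatment although that infusion is withheld.

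The cost is SAP text and programming; the dates are already collected. The downside is that completers are carried some days past their last infusion (about one week to Day 162, two to Day 169). No qualifying pre-infusion sUA can occur in that time. A late infusion reaction classified at the investigator's discretion (Protocol 9.6.1.2.1.5) would count if it met the endpoint. A Week 22 visit later than the chosen day would not be covered.

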### 3.4.3 Exploratory Endpoint Analyses

## 3.5 Analysis of Pegloticase Pharmacokinetics, Methotrexate Polyglutamates, and Anti-Drug Antibodies

### 3.5.1 Pegloticase and MTX PK

Serum samples for pegloticase PK analysis will be collected approximately 15 minutes to 2 hours after the end of infusion on Day 1; prior to infusion and approximately 15 minutes to 2 hours after the end of the infusion at Weeks 2, 6, 12 and 20. An additional PK sample will be collected at the End-of-Study (Week 24)/Early Termination Visit.

PK summaries will be done for the PK analysis set. MTX polyglutamate summaries will be done for the mITT analysis set. All results will be presented by 'as assigned' infusion duration group.

The following presentations of subject serum pegloticase concentration data covered in this SAP will be provided for pegloticase:

- A listing including subject, week/time point (actual, planned), treatment and serum concentrations. End of infusion sampling times are expressed relative to the start time of infusion.
- A table summary of serum pegloticase concentrations at each time point (n; mean, SD, coefficient of variation (CV)% calculated as  $100\% \times SD/mean$ , minimum, 25th percentile, median, 75th percentile, maximum, geometric mean and geometric CV%) will be provided for the PK analysis set. Similar tables will be produced by Month 6 sUA responder status.

Further, the mean and CV% of pegloticase concentrations will be provided by visit in the subset of subjects who are ADA positive (defined as positive for anti-PEG or anti-uricase antibodies at any visit) and ADA negative (defined as negative for both anti-PEG and anti-uricase antibodies at all visits) for each visit.

All concentrations BLQ after the first pegloticase infusion will be imputed by half of LLOQ for the analysis summaries. The number of BLQ records will be summarized. Concentrations more than 17 days after the last infusion will be excluded from the summary.

Concentrations of MTX polyglutamate are measured for 5 active metabolites (MTX-PG1, MTX-PG2, MTX-PG3, MTX-PG4, MTX-PG5). The summary of individual 5 MTX polyglutamate values, PG1-2 (i.e., PG1 + PG2), PG3-5 (i.e., PG3 + PG4 + PG5), PG4-5 (i.e., PG4 + PG5), and total PG1-5 (i.e., PG1 + PG2 + PG3 + PG4 + PG5) over time for all mITT subjects, as well as by Month 6 sUA responders and Month 6 sUA non-responders will be provided. All concentrations BLQ are excluded from the analysis summaries. When calculating the sum over MTX-PGs, values of '<5' count as 0 in the sum.

A plot of the mean total PG1-5, and individual 5 MTX polyglutamate mean values over time will be provided for the mITT set by Month 6 sUA response status (responder vs. non-responder) for each infusion duration group.

A listing of MTX polyglutamate concentrations will be provided, showing the subject, treatment, visit, collection date and time, study day relative to first MTX treatment date, and the 5 MTX polyglutamate values along with total MTX polyglutamate values (PG1-5).

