##### **9.4.3.1.1 Study considerations for subjects ending pegloticase infusions prior to 24 weeks**

- Methotrexate, along with folic acid, will be discontinued at the time of cessation of pegloticase infusions prior to Week 24.
- All subjects will complete the End of Pegloticase Infusions Visit and should be encouraged to remain on study and attend all Follow-Up visits, including the 30-day Follow-up Email/Phone call, Week 24/End of Study/Early Termination and 3 Month Post-Treatment Follow-up Visits barring withdrawal of consent from study participation.
- Activities related to pre/post infusion monitoring or medication dispensation will not be completed once a subject has stopped pegloticase infusions. These activities include:
  - MTX compliance/reconciliation

- IR prophylaxis
- IR prophylaxis compliance
- Folic acid compliance
- Pegloticase infusion
- Pegloticase PK sampling
- Pre-infusion MTX Polyglutamate sampling
- MTX drug/dispensation related items

Post-Treatment Follow-up:

The intent is to obtain at least 3 months of follow up on each subject after cessation of pegloticase infusions. If the subject ends treatment early but remains in the study and the 3-month Post-Treatment Follow-up Visit occurs prior to Week 24, the 3-month Post-Treatment Follow-up Visit will be adjusted accordingly based on the timing of the last treatment.

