## **9.6.5 MTX Polyglutamate Measurements**

Blood samples will be collected prior to pegloticase infusion on Day 1, Weeks 14, 22, End of Pegloticase Infusions Visit (if applicable) and 24 Visits during the Pegloticase + MTX Period.

Each sample collection date and time will be recorded in source documents and the eCRF.

Detailed instructions regarding blood sample timing and handling are provided in the Laboratory Manual.

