### 3.6.4 Laboratory Tests

Laboratory test results, including urine albumin: creatinine ratio, will be summarized by treatment period, infusion duration group, and study visit. For summaries of visits during the

Pegloticase + MTX Period, only data collected within 30 days (inclusive) after the last dose of MTX or pegloticase will be included. Results from the 3 Month Follow-up visit will also be summarized.

Shift-from-MTX baseline tables for laboratory parameters by Common Terminology Criteria for Adverse Events (CTCAE) grade will be presented. For tests where the CTCAE criteria are available, grade will be assigned programmatically, and shift tables will be based on the derived CTCAE grade. The CTCAE version 4.03 will be used for these summaries. Laboratory test results without established CTCAE grading criteria will also be classified relative to the normal reference range (normal, low, or high) and summarized as shift tables.

Laboratory summaries will be provided for both safety (both treatment periods) and ITT analysis sets (MTX Run-in Period only). Shift tables and change from baseline will be reported using the following baseline visits and periods:

- MTX Run-in Period: summarized for ITT analysis set using MTX baseline
- MTX Run-in Period and Pegloticase + MTX Period: summarized for safety analysis set using MTX baseline
- Pegloticase + MTX Period: summarized for safety analysis set using pegloticase baseline

A summary of elevated liver function test values, Hy's law, and subjects meeting MTX intolerance criteria (hematology only) will be provided for the safety analysis set by visit and overall for the MTX Run-in Period and the Pegloticase + MTX Period. Analyses of liver function tests and MTX intolerance criteria (hematology only) will also be done for the ITT for only the MTX Run-in period.

- alanine aminotransferase > ULN, 2xULN, 3xULN, 5xULN, 10xULN, and 20xULN
- aspartate aminotransferase > ULN, 2xULN, 3xULN, 5xULN, 10xULN, and 20xULN
- alkaline phosphatase  $\geq$  1.5xULN, 2.5xULN, and 3xULN
- total bilirubin  $\geq$  1.5xULN, 2xULN, and 3xULN

Hy's law:

- (alanine aminotransferase or aspartate aminotransferase > 3xULN) and total bilirubin  $\geq$  2xULN on the same date
- (alanine aminotransferase or aspartate aminotransferase > 3xULN) and total bilirubin  $\geq$  2xULN and alkaline phosphatase < 2xULN on the same date

MTX intolerance criteria (hematology):

- WBC  $<$  3.5  $\times$  10^9/L

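### Methotrexate polyglutamate is shown by Month 6 response with no on-methotrexate restriction; if stopped subjects are sampled, Week 24 totals in those non-responders reflect time off drug

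*SAP*

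**What the plan says.** **The display.** SAP 3.5.1 states that "MTX polyglutamate summaries will be done for the mITT analysis set". Five metabolites and several sums, including the total, are tabulated "over time for all mITT subjects, as well as by Month 6 sUA responders and Month 6 sUA non-responders will be provided". A plot of the mean total and the individual metabolites "will be provided for the mITT set by Month 6 sUA response status (responder vs. non-responder) for each infusion duration group". No on-MTX condition is given. Individual values below the limit of quantification are excluded, but results reported as below 5 count as zero in the sums.

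**Off-drug cuts elsewhere in the SAP.** For pegloticase, the same section says "Concentrations more than 17 days after the last infusion will be excluded from the summary". For laboratory summaries in the Pegloticase + MTX Period, SAP 3.6.4 says "only data collected within 30 days (inclusive) after the last dose of MTX or pegloticase will be included".

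**What happens on stopping.** Protocol 9.3 stops treatment after two consecutive pre-infusion sUA values above 6 mg/dL from Week 2, and keeps the subject on study through Week 24. SAP 3.4.2.1 counts these subjects as non-responders. Protocol 9.4.3.1.1 adds: "Methotrexate, along with folic acid, will be discontinued at the time of cessation of pegloticase infusions prior to Week 24".

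**Sampling after stopping.** Protocol 9.4.3.1.1 lists "Pre-infusion MTX Polyglutamate sampling" among the activities not carried out once infusions have stopped. Protocol 9.6.5 says: "Blood samples will be collected prior to pegloticase infusion on Day 1, Weeks 14, 22, End of Pegloticase Infusions Visit (if applicable) and 24 Visits". SAP 1.4.3 repeats that schedule. The row in the Schedule of Assessments carries five marks, which fits the same five occasions, although column alignment is lost in the text available. SAP Table 4 assigns End of Pegloticase and early termination samples to visits: days 2–127 to Week 14, days 128–162 to Week 22, and day 163 onwards to Week 24.

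**The concern.** One event, meeting the sUA rule, both defines non-response and ends MTX. A polyglutamate value taken afterwards is therefore partly a consequence of non-response. A by-response plot that includes such values could show lower totals in non-responders even if exposure on treatment had been identical.

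Protocol 7.2 gives MTX co-therapy as the means of reducing anti-drug antibodies and infusion reactions, so a gap at Week 24 would invite the reading that low MTX exposure led to loss of response. The planned listing gives study day from the first MTX dose, not days since the last, so a reader could not readily see the cause.

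The sampling conflict matters separately. Sites may follow different sections, and the two readings leave different subjects in the comparison.

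**Working it through.** The documents give no figure for this analysis, so there is none to reproduce.

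**1. Days off MTX at Week 24.** Inputs: Week *k* falls on day 7*k* + 1 and Week 24 on day 169 (SAP Table 1). MTX is taken 1 to 3 days before an infusion (Protocol 9.5.2); I take 2. The earliest stop under the sUA rule is Week 4. For a subject stopped at Week *k*, before that infusion, the last dose is on day 7*k* − 1, so days off = 169 − (7*k* − 1) = 170 − 7*k*.

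| Stop at Week | Days off MTX at Week 24 |
|---|---|
| 4 | 142 |
| 8 | 114 |
| 12 | 86 |
| 16 | 58 |
| 20 | 30 |
| 22 | 16 |
| Completer, last dose Week 23 (day 162) | 7 |

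**2. Size for the sums, with no true difference.** Assumptions not in the documents: half-life *h* of 1, 2 or 4 weeks, and a share *f* of sampled non-responders who had stopped, evenly over *k* = 4, 6, …, 20. To the nearest week, time off drug is 24 − *k*.

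- Mean residual in stopped subjects, relative to the on-drug level: average of 0.5^((24 − *k*)/*h*) = 0.009, 0.055, 0.181.
- Completers are themselves one week off drug, at 0.5^(1/*h*) = 0.50, 0.71, 0.84.
- Ratio of stopped subjects to completers, *r*: about 0.019, 0.078, 0.216.
- Ratio of non-responders to responders: 1 − *f* + *f*·*r*.

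| *f* | *h* = 1 week | *h* = 2 weeks | *h* = 4 weeks |
|---|---|---|---|
| 1.0 | 0.02 | 0.08 | 0.22 |
| 0.5 | 0.51 | 0.54 | 0.61 |
| 0.25 | 0.75 | 0.77 | 0.80 |
| 0 (no sample after stopping) | 1.00 | 1.00 | 1.00 |

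**3. Individual metabolites.** Illustration with an assumed lognormal metabolite (median 20 on MTX, log-SD 0.5) and a limit of 5. If levels fall to 10%, the true mean is about 2.3 and 97% of values are below the limit. Excluding those gives a mean of about 6.2; counting them as zero gives about 0.2. The sums therefore carry the fall, while the metabolite means cannot drop below the limit and rest on the few highest values.

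**4. Week 14.** An End of Pegloticase visit after a Week 4 stop falls near day 29, which Table 4 assigns to Week 14 if there is no nominal sample. By then the subject has had about 7.7 weeks of MTX: (27 + 27)/7, with MTX started on day −27 counting through zero and last taken on day 27. A continuing subject has had 4 + 14 = 18 weeks. That sample is only about 2 days after the last dose, so a days-since-dose cut would not remove it.

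**5. The other reading.** If nothing is sampled after stopping, *f* = 0 and the Week 24 distortion disappears. Subjects who stop before Week 14 then contribute Day 1 only.

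**The case against.** The strongest reply is that Protocol 9.4.3.1.1 is the provision written for subjects who end infusions early, and it stops this sampling. Followed to the letter, it removes the bias. That stands, and it makes the point conditional. It does not settle the matter: Protocol 9.6.5 and SAP 1.4.3 schedule a sample at a visit that exists only for early stoppers, and Table 4 assigns those samples to analysis visits. Nor does the pre-infusion label separate the two cases, since Table 4 uses that label for these same visits. Pegloticase sampling is also on the list of stopped activities, yet the SAP still gives it a 17-day cut.

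A reader might infer that Week 24 values in non-responders as a group are low by construction. The documents do not support that. Some non-responders fail on time below 6 mg/dL in Month 6 and may still be taking MTX. MTX can be stopped while the subject stays in the study (Protocol 9.1), and subjects who stop pegloticase for other reasons can still be responders (SAP 3.4.2.1), so time off MTX is not confined to non-responders. The fall is clear only for the sums.

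A reader might also infer that the display is meant to test whether MTX exposure goes with response. No visible objective or endpoint says so, and SAP 3.1.1 rules out inferential testing. Day 1, Week 14 and Week 22 are shown beside Week 24.

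**Conclusion.** The concern holds in conditional form. If samples are taken after stopping, Week 24 polyglutamate sums in non-responders who stopped measure time off MTX rather than exposure during treatment, and individual-metabolite means are distorted differently by the exclusion of values below the limit. If they are not taken, this bias is absent, but early stoppers leave the comparison after Day 1. The conflict between the protocol sections is real on either reading.

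For the sums, the downward direction in stopped subjects does not depend on the assumed half-life. The size does, and it also depends on the share who stopped; neither is in the documents. The figures of 2%, 8% and 22% are the extreme case in which every sampled non-responder stopped over Weeks 4 to 20. The display is exploratory and descriptive, and primary and secondary endpoints are unaffected. The change is still worth making, because the same section already applies the equivalent safeguard to pegloticase.

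**What to change.** 1. Reconcile Protocol 9.4.3.1.1 with Protocol 9.6.5, the Schedule and SAP 1.4.3 on whether the End of Pegloticase and Week 24 samples are taken after infusions stop.
2. In SAP 3.5.1, limit the by-visit and by-responder polyglutamate tables and plots to samples within a stated number of days of the last MTX dose. Show off-MTX samples separately and add days since last MTX dose to the listing. Candidate limits are 10 days (weekly dosing plus the 3-day visit window) or the 17 days already used for pegloticase. Each has a cost. A completer who doses 3 days before the Week 22 infusion (day 152) and a week later (day 159) is 10 days off at day 169, or 13 with a visit 3 days late, and would be lost under the 10-day limit. A Week 22 stop, about 16 days off, would be kept under the 17-day limit.
3. Do not move early End of Pegloticase samples (days 2–127) into Week 14 through Table 4; show them as their own time point.

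The cost is a short SAP amendment and a protocol clarification. MTX dose dates are already recorded in the eCRF (Protocol 9.5.11). The downside is fewer non-responders at later visits, so the table should show the number contributing at each visit.
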